1.3.2 Part 2: Study schedule of assessments (Periods 1 and 2)

Study Period Day (D) or Week (W) (allowed range)	Screening ^a D-60 to D-1	Blinded Treatment Period							
		W0 D1 D2		W2 (±3 days)	W4 (±3 days)	W13 _u (±3 days)	W26 _u (±3 days)	W39 _u (±3 days)	W52 _{b,u} (±14 days)
Visit number	1	2	3	4	5	6	7	8	9
Site visit	X	X	X	X	X	X	X	X	X
Demography	X								
Informed consent	X								
Inclusion/exclusion criteria	X	X							X
GBA complete gene sequencing and LRRK2 G2019S genotyping ^{a,c}	X								
Medical/surgical history and PD history	X								
RBD history (if applicable) ^d	X								
Prior/concomitant medications	X	X	X	X	X	X	X	X	X
Randomization		X							
MRI ^{a,e} (without contrast)	X								
Lumbar puncture ^{a,e}		X ^f							X
Study treatment administration									
GZ/SAR402671 or placebo		qd							
Dispense IMP		X			X	X	X	X	X ^g
Dispense/check patient diary	X	X	X	X	X	X	X	X	X
Safety									
Physical examination	X	X					X		X
Neurological examination	X	X				X	X	X	X
Height	X								
Body weight	X								X
Archival blood sample ^h		X							
Vital signs, body temperature ⁱ	X	X	X	X	X	X	X	X	X
Hematology and biochemistry	X	X		X	X	X	X	X	X
Urinalysis	X	X		X	X	X	X	X	X
Serum β-HCG pregnancy test (for WOCBP)	X								

Study Period Day (D) or Week (W) (allowed range)	Screening ^a	Blinded Treatment Period							
	D-60 to D-1	W0		W2 (±3 days)	W4 (±3 days)	W13 _u (±3 days)	W26 _u (±3 days)	W39 _u (±3 days)	W52 _{b,u} (±14 days)
	D1	D2							
Visit number	1	2	3	4	5	6	7	8	9
Urine pregnancy test (for WOCBP)		X				X	X	X	X
Ophthalmology exam ⁱ	X				X	X	X	X	X
12-lead ECG	X				X		X		X
Adverse event collection	X	X	X	X	X	X	X	X	X
Biomarkers									
Biomarkers: CSF ^k		X ^f							X
Biomarkers: serum and plasma ^l		X		X	X	X	X	X	X
GCase: dried blood spot ^{a,m}	X								X
DNA (optional) (Not applicable in Israel)									
Pharmacogenetics DNA sample ⁿ		X							X
Pharmacokinetics									
Plasma samples		X ^o	X	X			X ^o		X ^o
CSF samples		X ^{f,p}							X
Assessments^q									
DAT scan ^{a,e}		X (Pre-dose) ^{e,r}							X
MDS-UPDRS (including H&Y)	X ^s	X				X	X	X	X
PD-CRS	X	X				X	X	X	X
MoCA	X	X				X	X	X	X
SDMT (oral)		X				X	X	X	X
TMT-A; TMT-B		X				X	X	X	X
BDI-II	X ^t	X		X	X	X	X	X	X
CGI		X							X
PGIC						X	X	X	X
PDQ-39		X				X	X	X	X
EQ-5D		X				X	X	X	X
FES		X				X	X	X	X
HRPQ		X				X	X	X	X

Abbreviations: α -Syn: α -synuclein; β -HCG: beta-human chorionic gonadotropin; AE: adverse event; BDI-II: Beck Depression Inventory, second edition; CGI: Clinical Global Impression; CSF: cerebrospinal fluid; DAT: dopamine transporters; DAT scan, ioflupane I-123 injection DaTSCAN; DBS: dried blood spot; ECG: electrocardiogram; EQ-5D: EuroQol Five Dimensions questionnaire; FES: Falls Efficacy Scale; GBA: glucocerebrosidase gene; GCase: glucocerebrosidase; GL-1: glucosylceramide; H&Y: Hoehn and Yahr; HRPQ: Health-Related Productivity Questionnaire; IMP: investigational medicinal product; LP: lumbar puncture; lyso-GL 1: glucosylsphingosine; MDS-UPDRS: Movement Disorder Society-Unified Parkinson's Disease Rating Scale; MoCA: Montreal Cognitive Assessment; MRI: magnetic resonance imaging; NFL: neurofilament light chain; PD: Parkinson's disease; PD-CRS: Parkinson's Disease-Cognitive Rating Scale; PDQ-39: Parkinson's Disease Questionnaire - 39; PGIC: Patient Global Impression of Change; PK: pharmacokinetics; qd, daily; RBD: rapid eye movement sleep behavior disorder; SDMT: Symbol Digit Modalities Test; TMT-A: Trail Making test A; TMT-B: Trail Making test B; WOCBP: women of childbearing potential.

- a For patients who have previously completed Part 1, the following will NOT have to be repeated: GBA mutation and LRRK2 screening, GCase: dried blood spot, MRI, LP, and DAT scan.
- b This visit will serve as the screening for patients enrolling into Period 3.
- c Genetic screening will not need to be repeated to confirm eligibility of patients from Part 1 to enroll in Part 2. Once the results of the GBA gene sequencing (positive for a GBA mutation) and the LRRK2 genotyping (negative for the G2019S mutation) are confirmed, the remaining of the screening activities can continue.
- d Confirmed by historically documented polysomnography or by RBD screening questionnaire.
- e Once patients demonstrate eligibility based on screening criteria, MRI, LP, and DAT scan will be performed, except for the patients who completed these baseline assessments in Part 1. Baseline MRI must be done at least 7 days prior to the end of the screening period (Day -8). DAT scans will be performed only in countries where it is approved.
- f The LP may be done during the screening period within 14 days prior to randomization (Day -14 to Day -1) or on the day of randomization (Day 1, pre-dose). Only one LP will be performed, during screening or at Day 1. If the baseline LP coincides with the baseline MRI, MRI must be done prior to LP. LP at baseline will not be required to confirm eligibility of patients from Part 1 to enroll in Part 2.
- g This dispensing is only for patients moving on to Period 3.
- h This sample will be collected and stored for use if any unexpected safety issue occurs to ensure that a preadministration baseline value is available for previously nonassessed parameters (eg, serology). This sample will not be required for patients from Part 1 to enroll in Part 2.
- i Multiple assessments occur on this study day. In addition to body temperature, other vital signs to be captured include: respiratory rate, heart rate, systolic, and diastolic blood pressure. Orthostatic vital signs will be done at screening, Weeks 4 and 52; at all other time points, vital signs will be done in the supine position.
- j Full ophthalmology examination and photography must be done during screening and at Week 52, early withdrawal or treatment discontinuation, as applicable. Visual acuity check, slit lamp examination and fundoscopy without pupil dilation are only required at Week 4, Week 13, Week 26, and Week 39. Pupil dilation/full evaluation can be performed at any time if deemed medically necessary. At Visits 1, 6, 7, 8, and 9, when neurological and ophthalmological examinations are performed on the same day, the neurological examination should be performed **before** the ophthalmological examination.
- k Cerebrospinal fluid biomarkers, including GL-1, lyso-GL-1, α -Syn, NFL, tau, phospho-tau, as well as beta-amyloid (1-40, and 1-42).
- l Plasma or serum biomarkers, including plasma GL-1, lyso-GL-1. With respect to an unscheduled visit, plasma or serum biomarker samples should only be taken if the patient has a known AE.
- m One whole blood sample will be collected and spotted on cards at the clinical site and both the sample and the card must be sent to the laboratory doing the genetic testing.
- n DNA sample will be stored to support possible future investigation of potential biomarkers for response to GZ/SAR402671. The patient must sign a separate and optional consent form for pharmacogenetics (DNA) analysis only. Of note, the first DNA sample should be collected at baseline after eligibility criteria are met, but it may be collected at any visit during the study. This sample will not be required for patients from Part 1 to enroll in Part 2. The second DNA sample should be collected at Week 52 or at any visit after Week 52.
- o Multiple plasma PK assessments occur on this study day. See detailed flowcharts in [Section 1.4.2](#) for timing of assessments.
- p Cerebrospinal fluid PK assessments. See detailed flowcharts in [Section 1.4.2](#) for more detail with respect to the timing of assessments.
- q Baseline efficacy assessments should be conducted **prior to GZ/SAR402671 administration on Day 1**. For patients already on PD medications at the time of randomization, all efficacy assessments must be done in the patient's "OFF" state (no PD medication may be taken for at least 12 hours prior to the first efficacy assessment). See also footnote s.
- r Baseline DAT scan may be done within 7 days prior to randomization (Day -7 to Day -1) or on the day of randomization (Day 1 pre-dose).
- s Baseline H&Y for patients on a stable dose of PD medication must be done on the "ON" state (see inclusion criterion [I 05](#)).
- t At screening, patients with BDI-II of 20-28, inclusive, should be evaluated by a mental health specialist before the Investigator can determine if the patient would be able to fully participate in the trial. Patients with a BDI-II of >28 (severe depression) at screening will be excluded.
- u Visit window extended up to 3 months, during Covid-19 outbreak ([Section 10.1.2](#)).

Note: When several items take place at the same time, the following order should be respected: vital signs; plasma sampling for pharmacodynamics, PK, and safety; LP, IMP administration.

Note: Pregnancy testing after screening will be by urine dipstick testing and **must** be conducted prior to imaging; pregnancy testing is required for all female patients capable of bearing children. Pregnancy tests may be performed more frequently in some countries due to local legislations related to WOCBP randomized in clinical trials.

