8.8 CONCOMITANT MEDICATION

A concomitant medication is any treatment received by the patient during the study aside from the IMP. Concomitant medications should be kept to a minimum during the study. Furthermore, changes in concomitant medications should be kept to a minimum and only occur if considered to be absolutely necessary in the medical judgment of the Investigator. However, if these are considered necessary for the patient's welfare and are unlikely to interfere with the IMP, they may be given as rescue medication at the discretion of the Investigator and must be recorded in the eCRF.

Concomitant medications, including over-the-counter, dietary supplements (eg, herbal remedies) or prescriptions, are permitted during the study period, except for ambroxol use which is forbidden throughout the study and the medications listed in the following sections (see [Section 8.8.1](#), [Section 8.8.1.1](#), [Section 8.8.2](#), and [Section 8.8.3](#)). Any treatment not permitted at study entry will be forbidden throughout the study.

Patients will be allowed to continue with their PD medication as usual, if on stable PD therapy at study start. However, it may be considered necessary in the medical judgment of the Investigator to initiate or intensify PD medications. In such occurrence, this could apply only to an immediate release levodopa formulation.

The definition of stable PD therapy according to the longstanding gold standard worldwide is:

- At least 30 days on levodopa or other PD therapy, including dopamine agonists.
- At least 60 days on rasagiline.

All concomitant medications reported at the time of the screening visit and for the duration of the patient's participation should be recorded.

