9.1.2 Part 2: Treatment phase

The primary endpoint is the change in MDS-UPDRS (PART II+III score; [Section 17](#) [[Appendix F](#)]), performed during the OFF state, from baseline to Week 52. Of note, Part IA, IB, and II of the MDS-UPDRS do not have separate ON or OFF ratings. The OFF definition provided in this protocol is to ensure uniformity among raters and the score sheets should document the OFF status associated with the Part III assessment.

The MDS-UPDRS will be performed for all patients at screening, on Day 1, and at Weeks 13, 26, 39, 52, 78, 104, 130, 156, 182, 208, and 216 by the certified blinded rater. No PD medication may be taken for at least 12 hours prior to efficacy assessments.

Analysis of the change from baseline to Week 52 and from baseline to Week 104, Week 156, and Week 208 in the 4 subscale scores will be performed as an exploratory endpoint.

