9.4.4 Levodopa or other Parkinson's disease therapy

9.4.4.1 Time to initiation/intensification of levodopa/PD therapy

It is anticipated that GBA-PD patients, if entering the study on a PD medication, will be able to remain on a stable dose of the PD medications for the entire duration of the study. However, it may be considered necessary in the medical judgment of Investigator to initiate or intensify PD medications. In such occurrence, this could apply only to an immediate release levodopa formulation. If PD medications are to be initiated or intensified, patients will be asked to return for an additional study visit on site. This also holds true if a patient requires a change in his/her PD medication. The Investigator will document any new medications or changes in medication at each study visit on the Concomitant Medication Log.

In Part 2 only, time to initiation of levodopa or other PD therapy (for patients not on levodopa/other PD therapy at baseline) or to increased dose of levodopa/other PD therapy (for patients on levodopa/other PD therapy at baseline) will be calculated.

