The examining neurologist/blinded rater will be responsible for conducting all the efficacy assessments and for determining the scores, and must be certified for MDS-UPDRS and PD-CRS rating prior to any involvement in the study. Throughout the study, the examining neurologist/rater must not be involved with any other aspect of patient care and management and must remain blinded to the patient's treatment and safety profile (AEs, concomitant medications and laboratory results). Moreover, he/she must also not read the protocol, ensuring accurate rater-blinded assessments. This person should instead refer to the schedule of assessments.

All other investigational site staff must refrain from discussing any aspects of the protocol and/or safety issues with the examining neurologist. The examining neurologist/blinded rater should maintain the role for a given patient throughout the study. The study site is responsible for appointing a backup examining neurologist/rater in the case the primary is unable to fulfill the

role and that person is responsible for conducting the remainder of the assessments for the patient throughout the remainder of the study. The role of the treating neurologist and the examining neurologist is NOT interchangeable throughout the study even for different patients.

The Clinical Coordinator may be a nurse or physician who will be responsible for coordinating and assisting all study site staff, including patient scheduling and completion and monitoring of all patients' case report forms. He/she will be responsible for coordinating IMP administration, and collect, process, and send all blood and other forms of biological samples and requests to the central laboratory. Additionally, he/she will be responsible for administering the patient-reported questionnaires, and coordinating the conduct of the baseline MRI (without contrast).

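### The OFF-state requirement is stated with two different scopes, and the narrower one, used in the flow charts given to raters, leaves out patients who start PD medication after randomisation

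*Protocol*

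**What the plan says.** Protocol Section 9.1.2 defines the primary endpoint as the change in MDS-UPDRS Part II+III "performed during the OFF state, from baseline to Week 52". It sets the population and the washout without reference to medication status at entry: "The MDS-UPDRS will be performed for all patients at screening, on Day 1, and at Weeks 13, 26, 39, 52" and later visits, and "No PD medication may be taken for at least 12 hours prior to efficacy assessments". The same section notes that only Part III carries an OFF status, which the score sheets should document; Part II has no separate ON or OFF rating.

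Footnote q of the Part 2 flow chart (Section 1.3.2) is narrower: "For patients already on PD medications at the time of randomization, all efficacy assessments must be done in the" OFF state. Footnote s of Section 1.3.1, footnote e of Section 1.3.3, and one sentence each in Sections 9 and 10.1 carry the same limit.

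PD medication can begin after randomisation. Section 8.8 says "it may be considered necessary in the medical judgment of the Investigator to initiate or intensify PD medications", and Section 9.4.4.1 repeats this; in both, only immediate-release levodopa may be used. Time to initiation is an exploratory endpoint.

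Section 10 says of the blinded rater: "Moreover, he/she must also not read the protocol, ensuring accurate rater-blinded assessments". The rater is directed to the schedule of assessments and is kept blind to concomitant medications.

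**The concern.** A patient who is untreated on Day 1 and starts levodopa by, say, Week 30 is covered by Section 9.1.2 but falls outside footnote q. The footnote is the only OFF rule in the document the rater is given. If that patient is rated while medicated at Week 52, a medicated score is compared with an unmedicated baseline, and the change is no longer the defined endpoint.

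The primary analysis would not remove the rating: Section 11.4.2.1 includes all data whatever the adherence to treatment and protocol. While five statements leave these patients out, it is also open to argument whether such a rating counts as a deviation at all. The endpoint at stake is the primary one, and footnote e carries the same wording through Period 3.

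**Working it through.** **The statements side by side**

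Limited to patients on PD medication at randomisation:
- Section 1.3.1, footnote s (Part 1)
- Section 1.3.2, footnote q (Part 2, Periods 1 and 2)
- Section 1.3.3, footnote e (Part 2, Periods 3 and 4)
- Section 9, first sentence
- Section 10.1, where the 12-hour sentence that follows is worded as a consequence of the limited one

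Not so limited:
- Section 5.2.3: OFF for patients receiving levodopa or other PD medication
- Section 6.5: 12-hour rule for visits with efficacy assessment
- Section 9, second sentence: 12-hour rule for any efficacy assessment
- Section 9.1.2: endpoint definition and 12-hour rule

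For a patient already treated at randomisation, both lists give the same answer. For a patient never treated, neither matters. They diverge only for a patient who starts PD medication on study. That group is foreseen: randomisation is stratified by PD medication use (Section 8.4), initiation is allowed, and its timing is an endpoint. The visit lists in Sections 10.1.2.6 to 10.1.2.9 remind patients not to take the study dose at home, but do not remind them to withhold PD medication.

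**The plan's own figure**

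Inputs from Section 11.1: difference 4.06, SD 10.01, two-sided alpha 0.05, power at least 80%, about 10% loss. The effect size is 3.25 / 8.01 = 0.406, and 0.406 × 10.01 = 4.06. A two-sample t calculation gives 97 per arm (power 80.2%), and 97 / 0.90 = 107.8, so 108 per arm. The stated size reproduces and has almost no spare power at 97 evaluable per arm.

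**Size of a possible bias**

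Let p be the share of an arm that started PD medication on study and was rated ON at Week 52, and g the mean number of points by which an ON rating is lower than an OFF rating. The drug's apparent advantage changes by

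shift = (p on placebo − p on active) × g.

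The protocol gives neither p nor g, so this cannot be evaluated. Purely for scale, with assumed values and power taken as Φ(Δ / (10.01 × √(2/97)) − 1.96):
- arm difference 0, any g: shift 0, Δ = 4.06, power 80.6%
- 0.05 × 3.25 = 0.16: Δ = 3.90, power 77.4%
- 0.10 × 5 = 0.50: Δ = 3.56, power 69.7%
- 0.15 × 10 = 1.50: Δ = 2.56, power 42.9%

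The last row is the least secure. Only Part III carries an OFF status, and only patients untreated at baseline can contribute to p, so a 15-point difference overall needs a larger one within that stratum. If more active than placebo patients were rated ON, the shift would have the opposite sign.

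**The case against.** The strongest reply is that the protocol, read as a whole, already requires OFF ratings for everyone. Section 9.1.2 is unrestricted, and so is the second sentence of Section 9, directly after the narrow one. This stands. A reader might infer from footnote q that the plan permits on-study starters to be rated ON and that the primary endpoint is therefore biased, perhaps with a large loss of power. The documents do not support that: an ON rating would breach Section 9.1.2, bias needs unequal frequencies between arms, and every input to a power loss would be assumed.

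It is also fair to say that the rater does not control the washout. It happens before the visit; the treating neurologist, who may read the protocol, monitors concomitant medications; and a patient starting PD medication is asked back for an extra visit at which the change can be recorded. Raters are certified, and the scale has its own ON and OFF definitions. These points reduce the risk considerably. They do not remove it, because site staff reading Section 10.1 meet the narrow rule too.

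Finally, this version is dated 09 February 2021, and Appendix U places the 52-week analysis in the first quarter of 2021. Rewording footnote q could then change little of the Week 52 data. That stands for data collection. It does not settle how ratings already made are classified, or what governs Period 3.

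**Conclusion.** There is a real but minor internal inconsistency. Five statements limit the OFF requirement to patients on PD medication at randomisation, while the endpoint definition and three other statements carry no such limit. The result is uncertainty about the rating condition for on-study starters at Weeks 13 to 52 and in Period 3, together with a primary analysis that would keep any non-OFF rating.

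The effect on the treatment difference can be anything from zero upward in either direction, depending on the difference between arms in such ratings and on the ON–OFF gap. The protocol gives neither, so no size is claimed; the figures under the check show scale only. Confidence is high in the inconsistency and low in any figure for its effect.

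**What to change.** Reconcile footnote s (1.3.1), footnote q (1.3.2), footnote e (1.3.3) and the limited sentences in Sections 9 and 10.1 with the sponsor's own endpoint definition in Section 9.1.2 and the wording of Section 5.2.3, so that one scope covers every patient taking PD medication at the time of the visit. Send raters and site staff a short note of the change.

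For ratings already made, use the OFF status on the Part III score sheets to identify those not done OFF, and list them among the deviation criteria for the per-protocol analysis in Section 11.4.2.1, which are to be documented before database lock. A separate additional MMRM is not needed, because that analysis already serves the purpose.

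The cost is five wording changes, one note and one entry in the deviation criteria. No new procedure or data collection is required.

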1.3.3 Part 2: Study schedule of assessments (Periods 3 and 4)

Study Period	Long-Term Follow-up Period (Period 3)												8-Week Follow-up Visit (Period 4)
	W65 ^f (±7 days)	W78 ^f (±7 days)	W91 ^f (±7 days)	W104 (2 years) ^f (±7 days)	W117 ^f (±7 days)	W130 ^f (±7 days)	W143 ^f (±7 days)	W156 ^f (3 years) (±7 days)	W169 ^f (±7 days)	W182 ^f (±7 days)	W195 ^f (±7 days)	W208 ^f (4 years) (±7 days)	
Visit number	9.1 (for Japanese patients only)	10	10.1 (for Japanese patients only)	11	11.1 (for Japanese patients only)	12	12.1 (for Japanese patients only)	13	13.1 (for Japanese patients only)	14	14.1 (for Japanese patients only)	15	16
Visit at clinical site	X	X	X	X	X	X	X	X	X	X	X	X	X
Concomitant medications	X	X	X	X	X	X	X	X	X	X	X	X	X
Study treatment administration													
GZ/SAR402671	qd												
Dispense IMP		X		X		X		X		X			
Dispense/check patient diary		X		X		X		X		X		X ^b	X ^b
Biomarkers^c													
Biomarkers: serum and plasma				X				X				X	
Safety													
Physical examination				X				X				X	X

Study Period	Long-Term Follow-up Period (Period 3)												8-Week Follow-up Visit (Period 4)
	W65 ^f (±7 days)	W78 ^f (±7 days)	W91 ^f (±7 days)	W104 (2 years) ^f (±7 days)	W117 ^f (±7 days)	W130 ^f (±7 days)	W143 ^f (±7 days)	W156 ^f (3 years) (±7 days)	W169 ^f (±7 days)	W182 ^f (±7 days)	W195 ^f (±7 days)	W208 ^f (4 years) (±7 days)	
Visit number	9.1 (for Japanese patients only)	10	10.1 (for Japanese patients only)	11	11.1 (for Japanese patients only)	12	12.1 (for Japanese patients only)	13	13.1 (for Japanese patients only)	14	14.1 (for Japanese patients only)	15	16
Neurological examination		X		X		X		X		X		X	X
Vital signs, body temperature	X	X	X	X	X	X	X	X	X	X	X	X	X
Body weight				X				X				X	
Hematology				X				X				X	
Biochemistry, urinalysis				X				X				X	
Urine pregnancy test (for WOCBP)		X		X		X		X		X		X	
Ophthalmology examination ^d		X		X		X		X		X		X	X
12-lead ECG				X				X				X	
Adverse event collection	X	X	X	X	X	X	X	X	X	X	X	X	X
Assessments^e													
DAT scan				X				X				X	

Study Period	Long-Term Follow-up Period (Period 3)												8-Week Follow-up Visit (Period 4)
	Day (D) or Week (W) (allowed range)	W65 ^f (±7 days)	W78 ^f (±7 days)	W91 ^f (±7 days)	W104 (2 years) ^f (±7 days)	W117 ^f (±7 days)	W130 ^f (±7 days)	W143 ^f (±7 days)	W156 ^f (3 years) (±7 days)	W169 ^f (±7 days)	W182 ^f (±7 days)	W195 ^f (±7 days)	
Visit number	9.1 (for Japanese patients only)	10	10.1 (for Japanese patients only)	11	11.1 (for Japanese patients only)	12	12.1 (for Japanese patients only)	13	13.1 (for Japanese patients only)	14	14.1 (for Japanese patients only)	15	16
MDS-UPDRS (including H&Y)		X		X		X		X		X		X	X
PD-CRS		X		X		X		X		X		X	
MoCA		X		X		X		X		X		X	
SDMT (oral)		X		X		X		X		X		X	
TMT-A; TMT-B		X		X		X		X		X		X	
BDI-II		X		X		X		X		X		X	X
PDQ-39		X		X		X		X		X		X	
EQ-5D		X		X		X		X		X		X	
FES		X		X		X		X		X		X	
HRPQ		X		X		X		X		X		X	

Abbreviations: AE, adverse event; BDI-II: Beck Depression Inventory, second edition; CGI: Clinical Global Impression; DAT: dopamine transporters; DAT scan, ioflupane I-123 injection DaTSCAN; ECG: electrocardiogram; EQ-5D: EuroQol Five Dimensions questionnaire; FES: Falls Efficacy Scale; GL-1: glucosylceramide; H&Y: Hoehn and Yahr; HRPQ: Health-Related Productivity questionnaire; IMP, investigational medicinal product; lyso-GL-1: glucosylsphingosine; MDS-UPDRS: Movement Disorder Society-Unified Parkinson's Disease Rating Scale; MoCA: Montreal Cognitive Assessment; PD: Parkinson's disease; PD-CRS: Parkinson's Disease-Cognitive Rating Scale; PDQ-39: Parkinson's Disease Questionnaire – 39; qd, daily; SDMT: Symbol Digit Modalities Test; TMT-A: Trail-Making Test A; TMT-B: Trail Making Test B; WOCBP: women of childbearing potential.

- a* This is the study completion visit, and it should be done 8 weeks after last IMP dose; this visit also applies to early withdrawal or treatment discontinuation, if applicable. This does not apply to patients who will transition to a long-term study with GZ/SAR402671 (last visit will be week 208).
- b* Retrieve patient diary. For patients transitioning to a long-term study with GZ/SAR402671 the patient diary will be retrieved at week 208.
- c* Plasma biomarkers, including plasma GL-1 and lyso-GL-1.
- d* After 52 weeks, the patient is required to have a full ophthalmological examination at Weeks 104, 156, 208, and early withdrawal or treatment discontinuation, if applicable. Visual acuity check, slit lamp examination and funduscopy without pupil dilation are only required at Weeks 78, 130, 182, and 216 (at the 8-week follow-up [Period 4] visit). Pupil dilation/full evaluation can be performed at any time if deemed medically necessary.
- e* For patients already on PD medications at the time of randomization, all efficacy assessments must be done in the patient's "OFF" state (no PD medication may be taken for at least 12 hours prior to the first efficacy assessment).
- f* Visit window extended up to 3 months, during Covid-19 outbreak ([Section 10.1.2](#)).

Note: Visits in Weeks 65, 91, 117, 143, 169, and 195 are for Japanese patients only.

